- 2. Time to OAC start: the time to first OAC initiation, as defined by the first fill date for apixaban, dabigatran, edoxaban, rivaroxaban, or warfarin. If there was no prescription fill for these medications, but the patient had 4 or more INR values measured over the study period, the date of the first INR measurement will be used for initiation of OAC.
- 3. OAC prescription coverage: the proportion of days that AF patients have OAC prescription fills over the duration of the study. The assumption is that a 30-day or 90-day supply will last for the planned period, even in the case of warfarin, when the length of time that a prescription lasts may be less well defined. Patients will only be included in this secondary analysis, if they had a prescription fill for apixaban, dabigatran, edoxaban, rivaroxaban, or warfarin.
- 4. OAC rates at follow-up: proportion of patients with an active oral anticoagulant dispensing at the end of the one-year follow-up. This will include patients with apixaban, dabigatran, edoxaban, rivaroxaban, or warfarin medication fills that encompass the end of the study period. If there was no prescription fill for these medications, this will also include patients with 4 or

more INR values measured over the study period, who had an INR value measured within 60 days of the end of the approximately one-year follow-up.

- 5. Rate of stroke or TIA: the incident rate of stroke or TIA related hospitalizations; stroke, excluding transient ischemic attacks (TIAs), will also be assessed
- 6. Rate of bleeding related hospitalization: the incident rate of hospitalizations for any bleeding
- 7. Health care utilization: the total counts of health care utilization (number of outpatient visits, emergency department visits, hospital admissions, etc.) for AF patients, including AF and non-AF related care
- 8. In-patient all-cause mortality: patients with in-hospital death
- 9. All-cause mortality: in a subset of patients with mortality status

XVI. STATISTICAL ANALYSES

A. DEMOGRAPHICS AND BASELINE CHARACTERISTICS

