All primary analyses will be based on modified intention-to-treat (mITT) principle (i.e., all identified early intervention patients who met eligibility and were mailed the intervention will be included; using “pseudo” wave assignments, all identified delayed intervention patients who met eligibility at the time of corresponding early mailings will be included). Since the additional exclusions after randomization will be applied in the same way, using the same time points for both the early and delayed intervention groups, we expect there will be no effect from these additional exclusions on the randomization. The mITT analysis will include the following:

- Early intervention members who were mailed a letter, with follow-up beginning on the date of mailing (up to two dates per site and the dates varied by site).
- Delayed intervention members who were not on treatment at the date of mailing (wave assignments were made for the delayed as described earlier in section I.F) with follow-up beginning on that date.

An as-randomized analysis will be performed for an incident occurrence of the primary endpoint as a sensitivity analysis (using a washout of 365 days). Randomization occurred prior to treatment status assessment per the study design. Therefore, the as-randomized analysis will include people who were on treatment as well as others who were not truly eligible for the study (e.g., had incomplete or invalid addresses or had a “do not contact” status).

Potential sensitivity analysis for mITT analysis: There may be differential loss to follow up between the early and delayed intervention groups because some members did not have valid mailing addresses, though we did not assess the addresses of the members in the delayed intervention arm at the time of early intervention mailings. It is not possible to retrospectively ascertain the address status of the delayed intervention group as of the date on which mailing would have occurred for that group. We can estimate the magnitude by referring to the early intervention group, and in the early intervention group, we can compare the baseline characteristics and experience of the individuals who had no valid address to those who do.

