OAC adherence will be assessed by the proportion of days covered by OAC prescription fills over the duration of the study, or the proportion of days covered among those patients dispensed an OAC. The assumption is that a 30-day or 90-day supply will last for the planned period, even in the case of warfarin, when the length of time that a prescription lasts may be less well defined. Overlapped dispensing days of the same drug will be counted only once, and the days prescribed beyond censor date will be censored accordingly in calculating the total days covered by OAC. Patients will only be included in this secondary analysis if they had a prescription fill for apixaban, dabigatran, edoxaban, rivaroxaban, or warfarin. Proportion of days covered will be summarized as mean (\pm SD), and median (25th, 75th percentiles) by early vs. delayed intervention, the comparison between the two groups will be conducted using Wilcoxon rank-sum test, as shown in Table 5 in Appendix A. Each Data Partner will run the SAS program(s) distributed by HPHCI, developed with the statistical team at Duke, to generate a summary table for their cohort of patients shown in Table 5 (there will be one for each Data Partner) and return the summary table to HPHCI. For entire study population, the effect size of two groups will be generated using meta-analysis methods.

3. Proportion of Patients Actively on OAC at the End of Follow-up

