OAC dispensing or first of 4 INRs at 42 days							
OAC dispensing or first of 4 INRs at 90 days							
OAC dispensing or first of 4 INRs at 183 days							

Table 2c. Odds ratio of filling at least one OAC dispensing or 4 or more INRs (primary endpoint) over the course of the 12-months of follow-up: early intervention vs. delayed intervention, by age, sex, and CHADS-VASC score in the modified intention to treat (mITT) analysis

	Early Intervention, n/N (%)	Delayed Intervention, n/N (%)	Unadj. Parameter Estimate (SE)	Unadj. Odd Ratio (95% CI)	Adj. Parameter Estimate (SE)	Adj. Odds Ratio (95% CI)	p-value for adjusted OR
OAC dispensing or first of 4 INRs – by sex							
Female							
Male							
OAC dispensing or first of 4 INRs – by age							
≤64 yrs							
65-74 yrs							
75-84 yrs							
≥85 yrs							
OAC dispensing or first of 4 INRs – by CHADS-VASC							
2-3							
4-5							
≥6							

Table 3. Hazard ratio of at least one OAC dispensing or 4 or more INRs (primary endpoint) at 12 months: early intervention vs. delayed intervention in the modified intention to treat (mITT) analysis

	Early Intervention, Cumulative incidence (95% CI)	Delayed Intervention, Cumulative incidence (95% CI)	Parameter Estimate (SE)	Hazard Ratio (95% CI)	p-value
OAC dispensing or first of 4 INRs at 365 days					
Met endpoint due to OAC					
Met endpoint due to 4 INRs					
Met due to 4 INR test PX codes (CPT)					
Met endpoint due to other code					

Kaplan Meier curves will be generated for analyses related to Table 3.

Table 4. Numbers and proportions of filling at least one OAC dispensing or 4 or more INRs (primary endpoint) over the course of the 12-months of follow-up in intervention arm: patients with provider letter vs. patients without provider letter in the modified intention to treat (mITT) analysis

	Patients with Provider Letter, n/N (%)	Patients without Provider Letter, n/N (%)	p-value
OAC dispensing or 4 INRs at 365 days			

Table 5. Proportion of days on an OAC during all follow up time, among those treated for at least 1 day: early intervention vs. delayed intervention in the modified intention to treat (mITT) analysis

	Early Intervention	Delayed Intervention	p-value
Total number			
Number of days on an OAC			
Mean (SD)			
Median			
Minimum			
25 th percentile			
75 th percentile			
Maximum			
Number of OAC dispensings			
Mean (SD)			
Median (Min, 25 th , 75 th , Max)			
Minimum			

25 th percentile			
75 th percentile			
Maximum			

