Mean proportion of days on an OAC			
Standard deviation			
Median proportion of days on OAC (range across sites)			
25 th percentile			
75 th percentile			
Proportion in each arm with ≥80% of follow up time covered by an OAC episode			

Table 6. Proportion of patients actively on OAC at the end of follow-up among those treated for at least 1 day: early intervention vs. delayed intervention in the modified intention to treat (mITT) analysis

	Early Intervention, n/N (%)	Delayed Intervention, n/N (%)	Parameter Estimate (SE)	Odds Ratio (95% CI)	p-value
Actively on OAC at the end of follow-up					

Table 7. Cumulative incidence of clinical endpoints during all follow up: early intervention vs. delayed intervention in the modified intention to treat (mITT) analysis

With / without Principal Discharge Diagnosis (PDX) Flag	Outcomes	Early Intervention, n/N (%)	Delayed Intervention, n/N (%)	Early Intervention, Cumulative incidence (95% CI)	Delayed Intervention, Cumulative incidence (95% CI)	p-value
Principal Discharge Diagnosis (PDX Flag) Only	Hospitalization for ischemic stroke or unknown stroke					
	Hospitalization for transient ischemic attack					
	Hospitalization for systemic embolism					
	Hospitalization for ischemic stroke, TIA, or systemic embolism					

With / without Principal Discharge Diagnosis (PDX) Flag	Outcomes	Early Intervention, n/N (%)	Delayed Intervention, n/N (%)	Early Intervention, Cumulative incidence (95% CI)	Delayed Intervention, Cumulative incidence (95% CI)	p-value
	Hospitalization for hemorrhagic stroke					
	Hospitalization for ischemic or hemorrhagic stroke					
	Hospitalization for ischemic or hemorrhagic stroke or systemic embolism					
	Hospitalization for any bleeding					
	Composite of ischemic stroke, hemorrhagic stroke, systemic embolism and hospitalization for any bleeding					
Ignore Principal Discharge Diagnosis (PDX) Flag	Hospitalization for ischemic stroke or unknown stroke					
	Hospitalization for ischemic stroke or transient ischemic attack					
	Hospitalization for systemic embolism					
	Hospitalization for ischemic stroke, TIA, or systemic embolism					
	Hospitalization for hemorrhagic stroke					

With / without Principal Discharge Diagnosis (PDX) Flag	Outcomes	Early Intervention, n/N (%)	Delayed Intervention, n/N (%)	Early Intervention, Cumulative incidence (95% CI)	Delayed Intervention, Cumulative incidence (95% CI)	p-value
	Hospitalization for ischemic or hemorrhagic stroke					

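### Days covered is divided by all follow-up but measured in starters only, so a difference in when patients start can appear as a difference in adherence

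*SAP*

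**What the plan says.** SAP II.D.2, headed OAC Adherence, defines the measure as "the proportion of days covered by OAC prescription fills over the duration of the study", and the sentence continues "or the proportion of days covered among those patients dispensed an OAC". The population is restricted: "Patients will only be included in this secondary analysis if they had a prescription fill for apixaban, dabigatran, edoxaban, rivaroxaban, or warfarin". The arms are compared by Wilcoxon rank-sum test. Each Data Partner returns its own Table 5, and an effect size is then meta-analysed across partners.

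Table 5 in SAP Appendix A is titled "Proportion of days on an OAC during all follow up time, among those treated for at least 1 day" and has a row for "Proportion in each arm with ≥80% of follow up time covered by an OAC episode".

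Protocol XV item 3 matches: "the proportion of days that AF patients have OAC prescription fills over the duration of the study". Protocol XVI.C repeats the restriction to patients with a fill.

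The clock is set elsewhere. SAP II describes the mITT set as "Early intervention members who were mailed a letter, with follow-up beginning on the date of mailing". SAP I.F starts delayed-arm follow-up on the corresponding early-mailing date. No section starts the denominator at the first fill.

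**The concern.** Patients found to be on OAC before the mailing are excluded, so starters begin follow-up with uncovered days. A patient who starts in month 6 and never misses a dose scores about 50%. The measure is not adherence, because waiting time counts as uncovered. It is not a randomized comparison of exposure either, because never-starters are dropped and starting happens after randomization.

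The intervention is a one-time mailing at the start of follow-up, so it could plausibly shift when patients start. The trial could then report a change in adherence when only the decision to start, or its timing, had changed. Both arms would also look poorly adherent in the 80% row, partly because of time before initiation.

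**Working it through.** **Inputs from the plan.** Initiation is 33% (delayed) and 38% (early) over one year, with 30% attrition and two-sided alpha of 0.05 (SAP I.G). The plan gives no figure for days covered.

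**Check on those inputs.** The continuity-corrected chi-square sample size for 33% against 38% is 1963, 2418 and 3401 per arm at 90%, 95% and 99% power. Divided by 0.7 this is 2805, 3455 and 4859, or totals of 5610, 6910 and 9718, which match the plan's table. (The protocol labels that table as unadjusted for dropout, yet it reproduces only after the division. This does not affect the present point.)

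**Formula.** For a starter on day s of T, with coverage A after first fill:

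measure = A × (T − s) / T

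With A = 80% and T = 365:
- start on day 30: 0.80 × 335/365 = 73.4%
- start on day 150: 0.80 × 215/365 = 47.1%

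Measured from first fill, both are 80%.

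**Ceiling on the 80% row.** Even with A = 100%, the row requires (T − s)/T ≥ 0.80, so s ≤ 0.2 × 365 = 73 days. With a constant starting rate giving 33% at one year, the share of delayed-arm starters after day 73 is (0.67^0.2 − 0.67)/0.33 = (0.923 − 0.67)/0.33 = 77%.

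**Arm level.** Assumptions: T = 365, mean A = 75% in both arms, and a constant starting rate in the delayed arm.

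- Delayed-arm mean start, with λ = −ln(0.67)/365: 1/λ − 365 × 0.67/0.33 = 911.4 − 741.1 = day 170.4.
- Delayed-arm measure: 0.75 × (365 − 170.4)/365 = 40.0%.
- Early arm, extra 5 points spread uniformly over the first w days: mean start = (0.33 × 170.4 + 0.05 × w/2)/0.38.
- Early arm, proportional hazards: HR = ln(0.62)/ln(0.67) = 1.19.

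| Timing of the extra starts | Early mean start (day) | Early measure | Difference, points |
|---|---|---|---|
| within 42 days | 150.7 | 44.0% | +4.0 |
| within 90 days | 153.9 | 43.4% | +3.4 |
| within 183 days | 160.0 | 42.1% | +2.1 |
| proportional hazards | 168.0 | 40.5% | +0.5 |
| second half-year | 184.0 | 37.2% | -2.8 |

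Varying A from 50% to 90% and T from 365 to 540 days gives +1.4 to +4.9 (front-loaded), +0.3 to +0.8 (proportional hazards) and -1.5 to -3.4 (late).

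**Test behaviour.** The illustration is a pooled Wilcoxon at 28,000 per arm (80,000 × 0.7 / 2) with identical coverage after first fill. It rejects in 100% of simulated trials when starts are front-loaded, and in about 20 to 30% under proportional hazards. When timing does not differ, rejection stays near 5%.

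**Same scenarios with all patients counted.** Mean coverage with never-fillers at zero is the initiation proportion times the starters' mean. The delayed arm is 0.33 × 40.0 = 13.2%. The early arm is 0.38 × 44.0 = 16.7%, 0.38 × 43.4 = 16.5%, 0.38 × 42.1 = 16.0%, 0.38 × 40.5 = 15.4% and 0.38 × 37.2 = 14.1%, in the order of the table. The early arm has more covered days in every row, including the last, where the starters-only measure points the other way.

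**The case against.** - **Labelling.** The listed objective is days covered, the protocol calls the outcome prescription coverage, and Table 5 speaks of days on an OAC. Only SAP II.D.2 says adherence. This stands, and a reader should not infer that the objective itself is worded as adherence. Relabelling alone would still leave a between-arm test in a subset selected after randomization.
- **Denominator.** II.D.2 does not state the first day of the denominator and offers a second phrasing. The mailing date is an inference, but Table 5 says all follow-up and the follow-up start is defined. The second phrasing names a population, not a start date.
- **Scenario dependence.** This stands. The shift needs different start timing, not merely more starters.
- **The planned test.** A pooled Wilcoxon is not planned. The plan runs it within each Data Partner and meta-analyses an effect size. Follow-up will also vary. The rejection rates are therefore illustrative, but the shift in means does not depend on which test is used.
- **First fill to censoring is not a neutral alternative.** The protocol's introduction says discontinuation is highest in the first months of therapy, so late starters, observed for less time, look better. Simulations gave both arms identical persistence and front-loaded the extra starts. They assumed that 30 to 50% stop early after a mean of 60 to 90 days, that the rest continue for 700 to 1500 days, and 30-day supplies. That denominator made the early arm look 1.1 to 2.0 points worse, with rejection in 70 to 97% of trials at 28,000 per arm. A fixed window after first fill rejected at about the nominal rate. This objection stands and shapes the fix.
- **Context.** Time to first fill, initiation by 42, 90 and 183 days, and active use at end of follow-up are all reported. They help a careful reader but do not correct the Table 5 comparison.

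**Conclusion.** The point holds for a secondary endpoint and leaves the primary conclusion untouched. As specified, the measure mixes start timing with adherence and compares arms among patients selected after randomization. Two parts need no timing assumption: the algebra, and the day-73 ceiling on the 80% row for 365 days of follow-up.

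The size does need assumptions. With 33% against 38%, 365 days and 75% coverage after first fill in both arms, the shift is about +2 to +4 points if front-loaded, +0.5 under proportional hazards and -2.8 if late. A reader might infer that the trial will report better adherence in the early arm. The documents do not support that: they give neither start dates nor adherence levels, and the sign can reverse. They support only that a difference in start timing would be reported as a difference in adherence.

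Table A lists II.D.2 among the adjusted analyses, but II.D.2 specifies no model, and baseline covariates would not remove a term that depends on the start date.

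**What to change.** Change SAP II.D.2, Table 5 and protocol XV item 3, and align protocol XVI.C.

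(a) Between-arm comparison: the proportion of follow-up days covered by OAC in all mITT patients, never-fillers as 0, from mailing or pseudo-mailing to censoring. Label it OAC exposure and attach the p-value here. Table 5 already collects means and standard deviations, so each Data Partner can supply a mean difference for the meta-analysis.

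(b) Adherence: among starters, the proportion of days covered over a fixed window after first fill, for example 180 days, in those with that much follow-up remaining. Put the 80% row on that window. Show it by arm descriptively, without a p-value or causal wording.

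The cost is a small change to the distributed program, using the same claims data, made before the Data Partners run it. The mean in (a) will be lower because most patients never start. Part (b) loses late starters. At exactly 365 days of follow-up, a 180-day window drops those starting after day 185, which under the constant-rate assumption is (0.67^(185/365) − 0.67)/0.33 = (0.816 − 0.67)/0.33, or about 44% of delayed-arm starters. The number dropped should be reported by arm.

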Baseline characteristics of eligible early and delayed intervention cohorts will be based on the claims data at the time of randomization. Frequency distribution and summary statistics for demographic and baseline variables will be presented by early intervention group, delayed intervention group, and for the overall study population. Key demographic and baseline variables to be summarized include: geographic region, age, sex, risk factors for stroke, risk factors for bleeding, and select comorbid conditions. Continuous variables will be summarized as mean (±SD) and median (25th, 75th percentiles); the comparison between the two groups will be conducted using Wilcoxon rank-sum test. For the continuous variables in combined study population, the mean will be summarized. Categorical variables will be presented as counts (percentages) and will be compared between groups by using Pearson's chisquare or Fisher's exact test, as appropriate.

B. RESPONSES FROM PROVIDERS

As part of the provider intervention materials, providers will have the opportunity to respond to the patient's health plan and give an explanation for why their patients were not being treated with OAC via a postage paid postcard. The data collected from these responses will be aggregated by rationale for non-treatment and reported as counts (percentages) by the coordinating center. Data will not be linked to specific patients or providers.

C. EFFECTIVENESS ANALYSES

The proportion of patients with evidence of at least one OAC medication fill over the course of the follow-up, the primary endpoint, will be summarized and compared between the early intervention and delayed intervention arms. The definition for OAC medication fill will be an OAC medication billing in the pharmacy claims or at least 4 INR tests billed in the laboratory claims (indicative of OAC use that was not billed through the pharmacy claims data). To evaluate whether the comprehensive evaluation and customized multilevel (patient-level and provider-level) educational interventions increases the rate of use of oral anticoagulants at one year post intervention, we will evaluate the odds ratio (i.e. the odds of an average patient in the early intervention group taking OAC at 1 year compared to the odds of an average patient in the delayed intervention group taking OAC at 1 year) using logistic regression to account for the effect of Data Ppartner and adjust for other potential baseline risk factors. ³⁸ We will

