present the odds ratio, 95% confidence interval, and p-value to show whether there is a difference in rate of use of OAC at one year post intervention between the early intervention and delayed intervention groups. Similarly, we will analyze the proportion of days covered with an OAC prescription fill over the course of the follow-up. Patients will only be included in this analysis, if they had a prescription fill for apixaban, dabigatran, edoxaban, rivaroxaban, or warfarin.

Event rates for the following secondary outcomes will be summarized by treatment group, as defined by claims data:

- Stroke or TIA
- Ischemic stroke or unknown stroke
- Hemorrhagic stroke
- Hospitalization for any bleeding
- Composite of ischemic or hemorrhagic stroke
- Composite of ischemic stroke, hemorrhagic stroke, and hospitalization for any bleeding

For time-to-event outcomes, Kaplan-Meier cumulative incidence estimates and log-rank test will be utilized. ³⁹ In addition, Cox proportional hazards model with early intervention vs. delayed intervention as main effect will be used to assess the clinical outcomes, after adjusting for baseline risk factors. ⁴⁰ A robust sandwich covariance estimate or a frailty model will be used to account for effect of Data Partner. The hazard ratio, 95% confidence interval and p-value will be presented to summarize the difference in the risk of clinical outcome between early intervention and delayed intervention group. Inhospital death or medically attended death will be collected through claims data. Analyses will be performed using SAS software version 9.4 or higher (SAS Institute, Inc., Cary, NC).

More details on the statistical methods and analyses will be provided in the SAP. The SAP will be finalized prior to study database lock, 12 months after at least 80% of the early intervention mailings. Of note, all patient-level data will be maintained by the Data Partners, so analyses are expected to be conducted via a distributed SAS programming code developed by the coordinating center and results are expected to be returned, by Data Partner, in aggregate to the coordinating center. Analyses will be examined by Data Partner and across Data Partners.

XVII. DISSEMINATION PLAN OVERVIEW

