For all tables below, the study coordinating center at HPHCI will receive Data Partner-specific tables (there will be one of each table per Data Partner). The coordinating center will generate aggregated tables for Data Partners (shown below), these will be shared with the Duke DCC statistical team. Duke DCC will have a data-use agreement with each Data Partner as necessary in order to receive/access aggregate summary data, which are housed at HPHCI. Duke DCC will conduct the meta-analysis across all study sites. No Data Partner-specific tables will be shared beyond the coordinating center and Duke DCC, if agreed upon by Data Partners, the analytic team; only data aggregated across sites will be published or made public.

Table A. Baseline covariates to be adjusted in the models described in sections II.C, II.D.1, II.D.2, II.D.3, and II.D.4

Demographics
Age (restricted cubic spline terms)
Sex (male vs. female)
Medical history
History of anemia (yes vs. no)
History of hypertension (yes vs. no)
History of diabetes (yes vs. no)
History of hospitalization for any bleeding (yes vs. no)
History of peripheral vascular disease (yes vs. no)
History of prior cerebrovascular disease (yes vs. no)
History of heart failure (yes vs. no)
History of kidney disease (yes vs. no)
History of MI
History of CABG
History of coronary stent
Bleeding risk score: ATRIA score (Low (≤ 3) vs. Intermediate (4) vs. High (≥ 5))
Hospitalization in the prior 6 months (0 vs. 1 vs. 2 vs. ≥ 3)

Table 1. Baseline characteristics of all patients in the modified intention to treat (mITT) analysis by early intervention vs. delayed intervention

	Overall (N=XXXX)	Early intervention (N=XXXX)	Delayed intervention (N=XXXX)	p- value	Stand. mean difference (%)
Demographics					
Age					
N					
Mean (SD)					
Median (Min, 25 th , 75 th , Max)					

	Overall (N=XXXX)	Early intervention (N=XXXX)	Delayed intervention (N=XXXX)	p-value	Stand. mean difference (%)
30-34 yr, %					
35-39, %					
40-44, %					
45-49, %					
50-54, %					
55-59, %					
60-64, %					
65-69, %					
70-74, %					
75-79, %					
≥ 80, %					
Sex					
N					
Female, %					
Region					
New England, %					
Mid-Atlantic, %					
South-Atlantic, %					
Midwest, %					
Mountain, %					
Pacific, %					
Unknown, %					
Medical history					
History of anemia?					
N					
Yes, %					
History of hypertension?					
N					
Yes, %					
History of diabetes?					
N					
Yes, %					
History of hospitalization for any bleeding?					
N					
Yes, %					

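### SAP II.D.2 gives only an unadjusted Wilcoxon test for days covered by OAC, although Table A assigns covariate adjustment to it, and the effect size to be pooled is not defined.

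*SAP*

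**What the plan says.** Four places bear on how days covered is analysed.

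- **SAP II.D.2 (OAC Adherence).** After listing summary statistics by arm, it says that "the comparison between the two groups will be conducted using Wilcoxon rank-sum test, as shown in Table 5 in Appendix A". Each Data Partner is to "generate a summary table for their cohort of patients shown in Table 5". The overall result is described in one sentence: "For entire study population, the effect size of two groups will be generated using meta-analysis methods". The analysis is limited to patients with a fill of one of five named anticoagulants.
- **SAP Appendix A, Table A.** The title reads: "Baseline covariates to be adjusted in the models described in sections II.C, II.D.1, II.D.2, II.D.3, and II.D.4". II.D.2 is named individually.
- **SAP Appendix A, Table 5.** There are two arm columns and a p-value column. The rows include the total number, "Mean proportion of days on an OAC", its standard deviation and quartiles. There is no column for an estimate, standard error or confidence interval.
- **Protocol XVI.C.** The primary endpoint is analysed "using logistic regression to account for the effect of" Data Partner and to "adjust for other potential baseline risk factors". The text then continues: "Similarly, we will analyze the proportion of days covered with an OAC prescription fill over the course of the follow-up".

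**The concern.** A programmer cannot follow both Table A and II.D.2. Table A requires a covariate-adjusted model for days covered, and II.D.2 and Table 5 leave no place for one. If this is not settled, either an adjusted or an unadjusted result could later be presented as the planned one.

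The gap matters more here than it would for an endpoint in the full analysis population. Having a fill is the outcome that the mailing is meant to change, so the two groups of starters need not be alike at baseline even though the arms were randomized. If the mailing brings in extra starters whose age, comorbidity or bleeding history predicts different persistence, an unadjusted comparison would report that mixture as an effect on adherence.

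The trial-wide result is also not pinned down. Patient-level data stay at the Data Partners for all or most analyses (SAP II.A), so the overall figure depends on what each partner returns. The Wilcoxon test as specified returns only a p-value.

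**Working it through.** The documents give no effect size, SD or power for days covered, so there is no planned figure to reproduce. The check has three steps.

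**1. Neighbouring sections side by side.**

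| Section | Model | Table A covariates | Provider clustering stated | Estimate returned |
|---|---|---|---|---|
| II.C primary | Logistic | Yes | Yes, GEE | Log OR and SE |
| II.D.1 time to OAC | Cox | Yes | Yes, robust SE | HR and 95% CI |
| **II.D.2 days covered** | **None** | **Only by Table A's title** | **No** | **None from the test** |
| II.D.3 active on OAC | Logistic | Yes | Yes, GEE | Log OR and SE |
| II.D.4 clinical outcomes | Cox | Yes | No | Log HR and SE |

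The general note before Table 2a says that, for Tables 2 to 9, partners produce unadjusted and adjusted model results. That makes it less likely that listing II.D.2 in Table A is a slip. The note is generic, however, since Tables 4 and 9 have no model either.

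**2. What can be pooled from Table 5.** With number, mean and SD by arm, each partner's crude difference is d = mean(early) − mean(delayed), with SE = sqrt(SD₁²/n₁ + SD₂²/n₂). These can be combined with inverse-variance weights. A crude mean difference can therefore be pooled. A covariate-adjusted one cannot, because no model estimate or SE is returned. SAP II.A names fixed-effects meta-analysis as the general method, but II.D.2 does not say what quantity is pooled, on which scale, or with which variance.

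**3. Illustrative size.** Inputs from the documents:
- 80,000 patients, 1:1, 30% attrition: 80,000 × 0.70 / 2 = 28,000 per arm
- OAC initiation of 33% (delayed) and 38% (early)
- Two-sided 5% test

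Assumed inputs:
- SD of the proportion of days covered 0.35 (range 0.30 to 0.40)
- A covariate-driven gap of 0.05 in expected coverage between the additional early-arm starters and the rest

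Calculation:
- Starters: 0.33 × 28,000 = 9,240 and 0.38 × 28,000 = 10,640
- Additional share of early-arm starters: 5/38 = 13%
- SE = 0.35 × sqrt(1/9,240 + 1/10,640) = 0.0050 (0.0043 at SD 0.30, 0.0057 at SD 0.40)
- Bias in the crude difference = (5/38) × 0.05 = 0.0066, or 1.3 SE
- Rejection probability with no adherence effect = Φ(bias/SE − 1.96) + Φ(−bias/SE − 1.96) = about 26% (34% at SD 0.30, 21% at SD 0.40)

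This refers to a z-test on the pooled crude mean difference. For one of five equal partners (an assumption), the SE is 0.0050 × sqrt(5) = 0.011 and the same formula gives about 9%. That z-test approximates the Wilcoxon test that II.D.2 would run at one partner.

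**The case against.** The strongest defence is that the firm conflict is one section number in a table title. The protocol's support rests on the single word 'similarly', the model it points back to is logistic for a binary endpoint, and the protocol defers details to the SAP. On that view II.D.2 is the controlling text and Table A needs a small correction. This limits how much weight the protocol can bear, but it does not remove the contradiction within the SAP.

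Four stronger readings are tempting, and the documents do not support them.

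- **That nothing can be pooled.** This is true of the Wilcoxon test as specified. Table 5 also returns number, mean and SD, and SAP Appendix D.1 allows other information from which weights can be calculated.
- **That this is the only comparison in a group formed after randomization.** Table 6's title carries the same restriction to patients treated for at least one day. That endpoint does have an adjusted model.
- **That II.D.2 alone ignores provider clustering.** II.D.4 states none either, and SAP II expects shared providers to be a small share of the population.
- **That the false-positive rate is very high.** A gap of 0.10 would give about 75% by the same formula, but it is hard to credit. If the Table A covariates explain 5% of the variance (assumed), their predictor has SD 0.35 × sqrt(0.05) = 0.078. A gap of 0.10 is then a shift of 1.3 SD in baseline profile. Even 0.05 is 0.6 SD.

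It is also fair to say that Table A contains no measure of motivation or past adherence, so adjustment cannot restore the balance that randomization gives.

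**Conclusion.** The point holds as an inconsistency in the SAP and an undefined pooled estimate. Table A assigns covariate adjustment to II.D.2 and the protocol implies it, while II.D.2 and Table 5 provide only summaries and an unadjusted test in patients with a fill. The promised effect size has no stated scale, variance or weights, and only a crude mean difference could be built from Table 5.

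Any imbalance in measured covariates among starters would remain in the result. Its size and direction are unknown from the documents. The 26% figure (21% to 34% over the SD range) shows only that a modest bias counts when each arm has about 10,000 starters. It rests on the assumed SD and gap and on testing the pooled crude mean difference.

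This is one secondary endpoint, and no sample size or decision rule depends on it. It should be corrected, but it does not threaten the primary analysis.

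**What to change.** In SAP II.D.2:

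- Make the between-arm analysis a linear model of each patient's proportion of days covered on arm plus the Table A covariates, fitted at each Data Partner by GEE with provider clusters and robust SE.
- Add the adjusted difference, its SE and 95% CI to Table 5.
- Pool the differences by fixed-effect inverse variance, and say that the scale is the difference in proportion of days. One scale should be fixed: a logit-type model would return log odds ratios, which cannot be pooled as differences.
- Keep the Wilcoxon test as a description within each partner.
- State that the comparison is conditional on a fill after randomization, and that adjustment deals with measured covariates only.

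The cost is SAP wording, extra Table 5 columns and one more model in the distributed program, using covariates already built for the primary analysis. The drawback is that a linear model of a bounded, skewed outcome relies on robust SE, which is acceptable with thousands of starters overall but should be checked at the smallest partner.

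If the team prefers no adjustment, the minimum repair is to remove II.D.2 from Table A's title, name the unadjusted mean difference as the pooled effect with its variance, and record the departure from what the protocol implies. That makes the plan consistent but leaves measured imbalance in the comparison.
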